1.6. Study Design

This study will be an open label, multi-cohort, phase II trial for the combination therapy of MEDI0457 (INO-3112) and Durvalumab (MEDI4736) in patients with HPV-16 and/or -18 related malignancies. This study will enroll 3 cohorts of patients with HPV-16/18 (+) tumors. The three cohorts are:

- 1. HPV-16/18 cervical cancer,
- 2. HPV-16/18 rare tumors (anal, penile, vulvar, vaginal), and
- 3. HIV (+) HPV-16/18 malignancies (any site).

Each cohort will have a two-stage design with predetermined stopping rules based on ORR after stage I and each cohort will function independently clinically. After each cohort completes accrual to stage I, only the two cohorts with the most responses will move on to stage 2.

Therefore, accrual to stage 2 will not start till all three cohorts have completed stage I. However, if a single cohort has a high response rate (≥4 responses out of 9 patients), the second stage of accrual may proceed prior to other cohorts completing stage I.

At the onset of the study, only patients with cervical, vulvar, or vaginal cancers will be enrolled for the first 3 slots. Once all 3 of these patients have completed the first 6 weeks of treatment, enrollment will be opened to all included cancer histotypes.

Both MEDI0457 and durvalumab treatment will continue until confirmed disease progression or unacceptable toxicity. Either treatment may be stopped by the investigator if a SAE is deemed to be related to that treatment while the other treatment continues.

The target population consists of male or female patients 18 years of age or older with recurrent or metastatic HPV 16- or 18-associated cancers with persistent or progressive disease (PD) after initial standard-of-care treatment and lacking a curative treatment option.

Eligible patients must have at least one "measurable target lesion"—according to RECIST version 1.1—that has not been previously irradiated. In addition, if the primary lesion is not large enough for a biopsy without changing radiologic findings for following response, one additional lesion

Version Number: 1.8 Date: July 26, 2019

Proprietary of MD Anderson Cancer Center

that can be safely biopsied at screening and prior to the first dose of MEDI0457 at Week 1 will be required.

All patients will receive combination treatment with MEDI0457 and durvalumab as per the **Planned Dosing Schedule (Section 4.4.1, Figure 1**, and **Table 3**).

[figure not shown]

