3.1. Inclusion Criteria

For inclusion in the study patients should fulfill the following criteria.

- 1. Written informed consent in accordance with institutional guidelines.
- 2. Male and female patients age 18 years or older who are able and willing to comply with all study procedures.
- 3. For patients who are not HIV positive, cervical, anal, penile, vulvar, or vaginal cancer positive for HPV-16 and/or HPV-18 by the institutionally approved assay. For patients who are HIV positive, histologically or cytologically confirmed diagnosis of cancer at any site that is positive for HPV-16 and/or HPV-18 by the institutionally approved assay. Tumors may be positive for more than 1 HPV subtype as long as HPV-16 and/or HPV-18

Version Number: 1.8

Proprietary of MD Anderson Cancer Center Date: July 26, 2019

is present. Note: For the first 3 patients, only cervical, vulvar, or vaginal cancers will be enrolled.

- 4. Patients with cancer that is refractory to standard therapy, that have either relapsed after standard therapy or has no standard therapy that increases survival by at least three months, and/or that are not curable by salvage approaches including resection and/or reirradiation.
- 5. Has measurable disease, defined as at least one lesion that can be accurately measured in at least one dimension (longest diameter to be recorded) with a minimum size of 10 mm by computed tomography (CT) scan, except lymph nodes which must have minimum short axis size of 15 mm (CT scan slice thickness no greater than 5 mm in both cases). Indicator lesions must not have been previously treated with surgery, radiation therapy, or radiofrequency ablation unless there is documented RECIST v1.1 progression in the lesion after such therapy.
- 6. All patients must consent to pre-treatment biopsy of the tumor if it can be done safely (as judged by the investigator) during screening. Week 10 on-treatment biopsies will be required for a minimum 10 patients. After 10 paired biopsies have been obtained then Week 10 on-treatment biopsy will be made optional.
- 7. World Health Organization (WHO)/Eastern Cooperative Oncology Group (ECOG) performance status of 0 or 1.
- 8. Adequate organ and bone marrow function within 28 days of Day 0. Criteria "a" to "c" cannot be met with recent (within 28 days of screening test except as noted below) blood transfusions or require ongoing growth factor support:

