3.4. Discontinuation of Investigational Product

An individual patient will not receive any further IP if any of the following occur.

- Initiation of subsequent anticancer therapy including another investigational agent.
- Confirmed PD: the initial assessment of PD by RECIST v1.1 (baseline PD assessment) will be confirmed by a repeat evaluation at the next tumor assessment time point, but no sooner than 4 weeks later. If any tumor assessment time point (beyond the first PD assessment) shows ≥ 20% increase in the overall tumor burden (the sum of diameters of target lesions and new lesions), when compared to the baseline PD assessment (the sum of diameters of target lesions and new lesions), the patient would be deemed as having confirmed PD and must be discontinued.
- An AE that, in the opinion of the Investigator, supporting company, or the MDACC IND Office, contraindicates further dosing.
- Patient experienced a DLT as defined in Section 6.7.2.
- Withdrawal of consent from further treatment with IP or lost to follow-up.

Version Number: 1.8 Date: July 26, 2019

Proprietary of MD Anderson Cancer Center

- Patient is determined to have met one or more of the exclusion criteria or failed to meet all of the inclusion criteria for study participation and continuing to receive IP might constitute a safety risk.
- Pregnancy or intent to become pregnant.
- Non-compliance with the study protocol that, in the opinion of the Investigator, supporting company, or the MDACC IND Office, warrants withdrawal from treatment with IP (e.g., refusal to adhere to scheduled visits).
- The treating Physician determines it is not in the best interest of the patient to continue.

At any time, patients are free to discontinue IP or withdraw from the study (i.e., IP and assessments) without prejudice to further treatment. If a patient is withdrawn from study, see Section 3.5.2.

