4.4. Doses and Treatments

4.4.1. Planned Dosing Schedule

All patients will receive combination treatment with MEDI0457 and durvalumab as per the following **Planned Dosing Schedule** (treatment should be given at the beginning of the week, unless otherwise specified) as detailed in **Figure 1** and **Table 3**.

Durvalumab will be administered at a fixed dose of 1500 mg q4wk for patients that are \ge 30 kg. For patients who weigh <30 kg, weight-based dosing will be used at a dose of 20 mg/kg q 4 weeks, and if their weight increases to \ge 30 kg they can be switched to durvalumab at 1500 mg every 4 weeks.

Patients will receive 7 mg MEDI0457 delivered by IM followed by EP on Day 1 (Week 1), Week 3, Week 7, Week 12 and then every 8 weeks until disease progression or unacceptable toxicity. Durvalumab will be administered on Week 4, Week 8, Week 12 and then every 4 weeks until disease progression or unacceptable toxicity. On days when both MEDI0457 and durvalumab administrations will occur on the same day (Week 12 then every 8 weeks), MEDI0457 will be administered first, and durvalumab IV infusion will start approximately 1 hour after MEDI0457 is delivered intramuscularly followed by EP.

Minimum time between Week 3 MEDI0457 dose and the Week 4 first durvalumab dose, and the Week 7 MEDI0457 dose and the Week 8 durvalumab dose is 7 days.

Version Number: 1.8 Proprietary of MD Anderson Cancer Center Page 1019 26 2019

4.4.2. **Durvalumab**

Durvalumab will be administered at a fixed dose of 1500 mg q4w in the combination and monotherapy arms for patients weighing \geq 30 kg. For patients weighing \leq 30 kg, the dose will be 20 mg/kg. The maximum number of doses of checkpoint inhibitor therapy will equal 13.

The duration will be approximately 1 hour (± 5 minutes) for each durvalumab infusion. A 1- hour observation period is required after the first infusion of durvalumab is administered. If no clinically significant infusion reactions are observed during or after the first dose, subsequent infusion observation periods can be at the investigator's discretion (suggested 30 minutes after each durvalumab infusion).

Patients will be monitored during and after the infusion with assessment of vital signs at the times specified in the study protocol.

See Section 6.7.1 dose administration changes in the event of Grade 1 or 2 infusion-related reactions.

4.4.3. **MEDI0457**

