- Serum Chemistry panel includes: albumin, alkaline phosphatase, ALT, AST, bicarbonate, calcium, chloride, glucose, lactate dehydrogenase, magnesium, potassium, sodium, total bilirubin (if Total bilirubin is $\ge 2x$ ULN [and no evidence of Gilbert's syndrome] then fractionate into direct and indirect bilirubin), total protein, creatinine, creatinine phosphokinase, blood urea nitrogen, uric acid, amylase and lipase. Please note: GGT to be collected at baseline and as clinically indicated.
- ^s Prothrombin time, APTT and INR.
- Free triiodothyronine (T₃) and free thyroxine (T₄) will only be measured if TSH is abnormal. They should also be measured if there is clinical suspicion of an AE related to the endocrine system.
- ^u Urinalysis panel includes: bilirubin, blood, glucose, ketones, pH, protein, specific gravity, and color/appearance.
- ^v Only for women of childbearing potential.
- To include luteinizing hormone and follicle-stimulating hormone only for women of child bearing potential who may be post-menopausal.
- x Patients with a negative serum pregnancy test within 3 days prior to Day 1 do not require a Week 1 Day 1 pregnancy test to be performed.
- y A window of ±3 days for all time points except C1D1. For Cycles 1 and 2, an interval of 7 days must occur between MEDI0457 and durvalumab treatments.
- ² MEDI0457 post-treatment reactions will be assessed 30 to 60 min after study treatment.
- ^{aa} A window of ± 3 days applies to all time points.
- bb Core tumor biopsies will be collected as per **Section 6.6.1**.
- cc ± 3 days. Biopsies at this time point are required until 10 subjects have provided tissue and then are optional for all subsequent subjects.
- dd At time of confirmed disease progression; Optional
- ^{ee} See **Section 6.6.2.1** for HPV Serology Research Blood details.
- ff Week 16 and then every 8 weeks until end of treatment.
- gg See Section 6.6.2.2 for Pharmacokinetics/ADA details.
- hh Week 16 only.
- ii For HIV(+) patients, viral load will be drawn at baseline, every month for the first 3 months, then every 3 months thereafter while on therapy.
- ^{jj} For patients with inactive Hepatitis B (Hep B core Ab(+)/HepB sAg (-)), HBV DNA and Hep BsAg will be monitored every month for the first 3 months, then every 3 months thereafter while on therapy.

Version Number: 1.8 Date: July 26, 2019 Proprietary of MD Anderson Cancer Center

STUDY ASSESSMENTS 6.

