Acetaminophen and/or an antihistamine (e.g., diphenhydramine) or equivalent medications per institutional standard may be administered prior to infusion at the discretion of the investigator for primary prophylaxis against infusion-related reactions. In the event of Grade ≤ 2 infusion-related reaction, the infusion rate of durvalumab may be decreased by 50% or interrupted until resolution of the event (up to 4 hours) and re-initiated at 50% of the initial rate until completion of the infusion. In patients experiencing Grade ≤ 2 infusion-related reaction, subsequent infusions may be administered at 50% of the initial rate. If a patient experiences an infusion-related reaction, acetaminophen and/or an antihistamine (e.g., diphenhydramine) and/or corticosteroid or equivalent medications per institutional standard may be administered prior to subsequent infusions at the discretion of the investigator for secondary prophylaxis of infusionrelated reactions. If the infusion-related reaction is Grade 3 or higher in severity, treatment with durvalumab will be discontinued.

As with any antibody, allergic reactions to dose administration are possible. Appropriate drugs and medical equipment to treat acute anaphylactic reactions must be immediately available, and study personnel must be trained to recognize and treat anaphylaxis. The study site must have immediate access to emergency resuscitation teams and equipment in addition to the ability to admit patients to an intensive care unit if necessary.

6.7.2. **Dose-limiting Toxicities**

Grading of DLTs will be according to the NCI CTCAE version 4.03.

A DLT will be defined as any Grade 3 or higher treatment-related toxicity that occurs during the DLT evaluation period (i.e., 4 weeks after the first dose of durvalumab is administered for the initial six patients), including the following treatment-related toxicities:

- a. Any Grade 4 irAE is a DLT.
- b. Any \geq Grade 3 colitis is a DLT.
- c. Any \geq Grade 3 non-infectious pneumonitis irrespective of duration is a DLT.
- d. Any Grade 2 pneumonitis that does not resolve to \leq Grade 1 within 3 days of the initiation of maximal supportive care is a DLT.
- e. Any \geq Grade 3 neurotoxicity (to include but not limited to limbic encephalitis, autonomic neuropathy, including peripheral neuromotor syndromes such as myasthenia gravis and Guillain-Barré) irrespective of duration is a DLT.

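### Enrolment opens to all histotypes about a week before the DLT period of the last of the first three patients ends, and the gate names no toxicity outcome

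*Combined protocol and SAP*

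**What the plan says.** Section 1.6 sets the restriction: "At the onset of the study, only patients with cervical, vulvar, or vaginal cancers will be enrolled for the first 3 slots". It lifts it with: "Once all 3 of these patients have completed the first 6 weeks of treatment, enrollment will be opened to all included cancer histotypes". The note to inclusion criterion 3 in Section 3.1 repeats only the restriction: "For the first 3 patients, only cervical, vulvar, or vaginal cancers will be enrolled". Neither place gives a DLT count, a review step or a consequence.

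The timing comes from three other places:

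- Section 4.4.1 gives MEDI0457 "on Day 1 (Week 1), Week 3, Week 7, Week 12 and then every 8 weeks until disease progression or unacceptable toxicity", and for the antibody says "Durvalumab will be administered on Week 4, Week 8, Week 12 and then every 4 weeks until disease progression or unacceptable toxicity". A footnote to Table 3 adds for durvalumab: "A window of ± 3 days applies to all time points".
- Section 6.7.2 defines the DLT evaluation period as "4 weeks after the first dose of durvalumab is administered for the initial six patients".
- Section 3.4 lists the events after which a patient receives no further investigational product. One is "Patient experienced a DLT as defined in Section 6.7.2".

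Section 8.1.3 holds the only numerical toxicity rule. It stops if the posterior probability that the DLT rate exceeds 30% is above 0.90, under a beta(0.6, 1.4) prior. The listed boundaries are 4/6, 6/12, 9/18, 11/24 and 13/30, and each cohort is monitored separately.

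**The concern.** Section 1.3.1 presents this as the first study of the combination in recurrent or metastatic HPV-16/18 disease, and the risk discussion in Section 1.4 accepts that toxicities may be additive or synergistic. The three-patient step is the only stagger on enrolment at the start of the trial. It is defined by time on treatment alone, and that time ends before the plan's own DLT period does. What is at stake is whether enrolment widens to every histotype on a partly observed DLT period, with no statement of what would be looked at first or what finding would hold enrolment back.

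**Working it through.** **1. The plan's toxicity rule reproduces.** With x DLTs in n patients, Pr(DLT rate > 0.30) = 1 − F(0.30; 0.6 + x, 1.4 + n − x), where F is the beta distribution function. The boundary is the smallest x that takes this above 0.90.

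| n | Boundary | Posterior at boundary | Posterior with one fewer DLT |
|---|---|---|---|
| 6 | 4 | 0.945 | 0.800 |
| 12 | 6 | 0.905 | 0.772 |
| 18 | 9 | 0.951 | 0.883 |
| 24 | 11 | 0.938 | 0.871 |
| 30 | 13 | 0.929 | 0.863 |

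All five boundaries match. Stopping probabilities at true rates 0.10, 0.20, 0.30, 0.40 and 0.50 recompute to 0.002, 0.033, 0.196, 0.555 and 0.875. Table 5 prints 0.002, 0.035, 0.196, 0.549 and 0.877. The rule is sound; the question is how the gate relates to it.

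**2. Calendar.** Week k begins on Day 7(k − 1) + 1, counting the first MEDI0457 dose as Day 1.

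- Gate: end of week 6 = 6 × 7 = Day 42.
- First durvalumab: Week 4 = 7 × 3 + 1 = Day 22.
- DLT period: 28 days, Day 22 to Day 22 + 27 = Day 49.
- Shortfall in the last-enrolled patient: 49 − 42 = 7 days. Observed: 28 − 7 = 21 days, or 75%.
- Durvalumab 3 days early (Day 19): period ends Day 46, 4 days short, 24 observed.
- Durvalumab 3 days late (Day 25): period ends Day 52, 10 days short, 18 observed.
- Week 7 MEDI0457: 7 × 6 + 1 = Day 43, one day after the gate. Table 3 also allows ±3 days for this dose (Day 40 to Day 46), so at best it comes two days before the gate.

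**3. Who is short.** The gate waits for all three patients. One who started d days before the last is at Day 42 + d when it opens and has finished the period if 42 + d ≥ 49, that is d ≥ 7. On the nominal schedule the shortfall is certain for the last-enrolled patient and applies to any who started less than 7 days earlier.

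**4. Can the gate be met after a DLT?** A patient with a DLT stops all investigational product under Section 3.4. If the gate means six weeks of treatment actually given, a DLT before Day 42 leaves it unmet. If it means six weeks elapsed, it opens whatever happened. The text does not choose.

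**5. Does the 0.90 criterion reach three patients?** The same formula at n = 3 gives 0.107, 0.490, 0.838 and 0.976 for 0, 1, 2 and 3 DLTs, so only 3/3 exceeds 0.90. No boundary is listed below six. Under Section 1.6, cervical cancer falls in one cohort, vulvar and vaginal cancer in another, and HIV-positive disease in a third. Under separate monitoring the three patients may therefore never be counted together.

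**6. What the step can still show.** The chance of at least one DLT in three patients is 1 − (1 − p)³ with the full period observed. If all three have only 75% of it, and onset is assumed uniform over the 28 days, it is 1 − (1 − 0.75p)³.

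| True DLT rate p | Full period | 75% in all three |
|---|---|---|
| 0.20 | 0.488 | 0.386 |
| 0.30 | 0.657 | 0.535 |
| 0.50 | 0.875 | 0.756 |

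**The case against.** The best defence is that the gate was never meant to carry the safety monitoring. The documents do not call it a safety lead-in; they restrict histology and then lift the restriction. Section 8.1.3 describes DLT monitoring as continuous and gives a probability criterion, so 3/3 in one cohort could be read as stopping the trial at once. A patient with a DLT stops treatment under Section 3.4, Appendix D governs dose modification, and Sections 7.2, 7.5 and 7.6 bring serious, special-interest and severe local or systemic events to the IND Office or the database within set times. A formal rule on three patients is a matter of preference. Figure 1 is not shown in the available text and might carry a condition.

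Much of this stands: the protections are real, and the absence of an n = 3 boundary is not in itself an error. It does not settle the timing, which follows from the plan's own schedule. Nor does it settle the reach of Section 8.1.3, which describes the monitoring both as continuous and as proceeding in groups of six, with the first toxicity report due after six evaluable patients per cohort. Counting the six weeks from first durvalumab would remove the shortfall, but treatment starts with MEDI0457 in Week 1, so that is not the natural reading.

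**Conclusion.** The point holds as a timing mismatch and an unstated decision rule. The gate falls about 7 days (4 to 10) before the DLT period closes in the last-enrolled patient and any who started within about 7 days of that patient. On the nominal schedule it also precedes the first vaccine dose given after durvalumab. The text does not say what happens if one of the three has a DLT, or whether the 0.90 criterion is applied to them. This rests on Day 1 being the first MEDI0457 dose and on nominal visit days with the 3-day window.

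Three stronger readings are tempting, and the documents do not support them.

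- A reader might infer that the step protects nobody. Even the last patient has 21 of 28 days observed, wider enrolment is delayed, and the individual rules apply throughout. At a true DLT rate of 30% the chance of seeing at least one DLT by the gate is still about 0.54 to 0.66, under the assumptions in the working.
- A reader might infer that enrolment opens even after three DLTs, or that it can never open after one. These rest on opposite readings of the same sentence, so only the ambiguity can be asserted.
- A reader might take the chance of two or more DLTs in three (35% at a true rate of 40%, 50% at 50%) as the rate at which the plan fails to act. A result of 2/3 gives 0.838, below the plan's own threshold. Only 3/3 in one cohort would meet it, with probability 0.027, 0.064 and 0.125 at true rates of 30%, 40% and 50%, given the full period.

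**What to change.** In Section 1.6 and in the note to criterion 3, replace the six-week condition with one tied to Section 6.7.2: enrolment opens to all histotypes when each of the first three patients has either completed the DLT evaluation period or had a DLT within it. This closes the timing gap and removes the doubt about a patient who stops treatment under Section 3.4.

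Then reconcile Sections 1.6, 3.4, 6.7.2 and 8.1.3 so that the text says whether the existing 0.90 criterion is checked on these three patients before enrolment opens and, if so, whether they are pooled across cohorts for that check. No new threshold is needed.

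Two related passages should be settled in the same edit. Section 6.7.2 defines the DLT period for the initial six patients, while Section 8.1.3 monitors DLTs in all 34. The first toxicity report is tied to 4 weeks of study treatment (Day 28), which covers only 28 − 21 = 7 days from first durvalumab.

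The cost is a few sentences and a delay of about one week (4 to 10 days), once. Sample size and the listed boundaries are unaffected.

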Figure 1. Overall Study Design Study Flow Chart

In the case that the first stopping boundary is crossed (Section 8.1.3), a Revised Dosing Schedule will be decided by the Principal Investigators, collaborators, supporters, and IND Office Medical Monitor and will be used for the remaining patients. Two options are to decrease the number of doses of vaccine given from a total of 3 to either 1 or 2 during the first 7 weeks and/or decrease dose of durvalumab to 750 mg Q4W. Other options may also be considered based on toxicity profile.

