6.7. Management of IP-related Toxicities

6.7.1. **Dose Management**

Either treatment may be stopped by the investigator while the other treatment continues. MEDI0457 doses should not be modified.

For AEs that are considered at least partly due to administration of durvalumab the following dose adjustment guidance may be applied:

- Treat each of the toxicities with maximum supportive care (including holding durvalumab).
- If the symptoms promptly resolve with supportive care, consideration should be given to continuing the same dose of durvalumab along with appropriate continuing supportive care. If medically appropriate, dose modifications are permitted for durvalumab.
- All dose modifications should be documented with clear medical reasoning and documentation of the approach taken.

In addition, there are certain circumstances in which durvalumab should be permanently discontinued (Appendix D, Postow 2015).

Following the first dose of durvalumab, subsequent administration of durvalumab can be modified based on toxicities observed (Appendix D, Postow 2015). All toxicities will be graded according to NCI CTCAE version 4.03.

Based on the mechanism of action of durvalumab leading to T-cell activation and proliferation, there is the possibility of observing irAEs during the conduct of this study. Potential irAEs include immune-mediated dermatitis, hepatitis/hepatotoxicity, endocrinopathy (hypothyroidism, hyperthyroidism, hypophysitis, and adrenal insufficiency), neuropathy/neuromuscular toxicity, nephritis, pancreatitis (elevated lipase/amylase), pneumonitis, and colitis. Patients should be monitored for signs and symptoms of irAEs. In the absence of an alternate etiology (e.g., infection or PD) signs or symptoms of dermatitis, hepatitis/hepatotoxicity, endocrinopathy

Version Number: 1.8

Proprietary of MD Anderson Cancer Center Date: July 26, 2019

(hypothyroidism, hyperthyroidism, hypophysitis, and adrenal insufficiency), neuropathy/neuromuscular toxicity, nephritis, pancreatitis (elevated lipase/amylase), pneumonitis, and colitis should be considered to be immune-related.

Dose modifications will not be required for AEs that are clearly not attributable to durvalumab (such as an accident) or for laboratory abnormalities that are not deemed to be clinically significant. Administration may continue despite concurrent vitiligo of any AE grade.

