8.1.1. Sample size estimate

Up to 77 evaluable patients will be enrolled in this study.

The design requires a maximum of 34 evaluable subjects per cohort. Nine subjects will be treated in the first stage. If 1 or fewer responses are seen, enrollment into that cohort will be stopped for futility. If there are 2 or more responses, an additional 25 subjects will be enrolled into the second stage. If there are 9 or more responses out of 34, the combination will be deemed worthy of further study. The two cohorts with the best response rates after completion of accrual into stage 1 for all 3 cohorts will move on to stage 2. The maximum total sample size is 77 (9 x 1 cohorts + 34 x 2 cohorts) evaluable subjects.

After each cohort completes accrual to stage I, only the two cohorts with the most responses will move on to stage 2. Therefore, accrual to stage 2 will not start till all three cohorts have completed stage I. However, if a single cohort has a high response rate (≥4 responses out of 9 patients), the second stage of accrual may proceed prior to other cohorts completing stage I.

Version Number: 1.8 Date: July 26, 2019 Proprietary of MD Anderson Cancer Center

8.1.2. **Efficacy futility assessments**

We will use a Simon's two-stage optimal design targeting an alternative hypothesis ORR of 0.35 versus a null hypothesis ORR of 0.15 with 80% power and a one-sided 0.05 significance level. This will be conducted independently in each of the three cohorts. ORR will be assessed every 8 weeks and will be defined using RECIST 1.1 criteria. During the interim, the accrual will be halted until the go/no-go decision can be made.

8.1.3. **Toxicity monitoring**

DLT will be monitored continuously in cohorts of 6 subjects for all 34 subjects to ensure safety using the methods by Thall et al. Cohorts will be monitored independently. The trial will be stopped early for toxicity if the $Pr(DLT > 30\% \mid data) > 0.90$ using a prior of beta (0.6, 1.4) for toxicity. Stopping boundaries corresponding to this probability criterion are to halt the trial if (# of patients with DLT) / (# patients evaluated) $\geq 4/6$, 6/12, 9/18, 11/24, and 13/30. The operating characteristics of this rule is found in table below.

Table 5. Operating Characteristics of Stopping Rules for Toxicity

True toxicity	P(stop)	p10	p25	p50	p75	p90	Avg # subjects	Avg # toxicities
0.10	0.002	34	34	34	34	34	33.9	3.4
0.20	0.035	34	34	34	34	34	33.2	6.7
0.30	0.196	12	34	34	34	34	29.9	9.0

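### Section 8.1.3 stops the trial when a toxicity boundary is crossed, but Section 1.6 continues on a Revised Dosing Schedule, and Table 5 describes only the first of these rules

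*Combined protocol and SAP*

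**What the plan says.** Section 8.1.3 monitors DLTs in groups of six, separately in each cohort, up to 34 patients. Its instruction is "The trial will be stopped early for toxicity" once the posterior probability that the DLT rate exceeds 30% is above 0.90, "using a prior of beta (0.6, 1.4) for toxicity". It then converts the criterion into counts: "Stopping boundaries corresponding to this probability criterion are to halt the trial if" the number with a DLT reaches 4/6, "6/12, 9/18, 11/24, and 13/30". It does not mention a change of schedule. Table 5 reports P(stop), quantiles of the number treated, average N and average toxicities.

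Section 1.6, in the text after Figure 1, cites Section 8.1.3 by number and gives a different consequence: "In the case that the first stopping boundary is crossed (Section 8.1.3), a Revised Dosing Schedule will be decided". The decision lies with the Principal Investigators, collaborators, supporters and the IND Office Medical Monitor, and the schedule "and will be used for the remaining patients". Two options are named and others are left open.

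No section explains how these statements fit together. The documents do not say whether DLTs seen before a revision still count, whether the boundaries restart, or whether a revision in one cohort applies to the others. They also do not say how responses before and after a revision count toward the 2/9 and 9/34 thresholds of Section 8.1.1.

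**The concern.** The same event leads to two different actions: one section ends accrual, the other carries on with a changed regimen. This is the plan's only quantitative toxicity stopping rule, for a combination that Section 1.3.1 describes as studied for the first time in this population. If the boundary were reached, those running the trial would hold two instructions. Anyone who had relied on Table 5 for the chance of stopping, or for the number of patients exposed to a toxic regimen, would have relied on figures for a rule that Section 1.6 does not follow.

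**Working it through.** **Inputs.** From Section 8.1.3: prior Beta(0.6, 1.4), threshold 30%, cut-off 0.90, looks at 6, 12, 18, 24 and 30 patients, maximum 34 per cohort. The DLT rate after a revision is not in the documents. It is assumed here to be either unchanged or halved.

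**Step 1: the boundaries.** With x DLTs in n patients the posterior is Beta(0.6 + x, 1.4 + n − x). The boundary is the smallest x with Pr(rate > 0.30) > 0.90.

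| Look | Boundary | Posterior probability | With one DLT fewer |
|---|---|---|---|
| 6 | 4 | 0.945 | 0.800 |
| 12 | 6 | 0.905 | 0.772 |
| 18 | 9 | 0.951 | 0.883 |
| 24 | 11 | 0.938 | 0.871 |
| 30 | 13 | 0.929 | 0.863 |

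All five stated boundaries reproduce.

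**Step 2: Table 5.** An exact binomial recursion over the five looks, with every crossing ending accrual permanently, gives:

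| True DLT rate | P(stop), Table 5 | P(stop), recomputed | Average N, Table 5 | Average N, recomputed |
|---|---|---|---|---|
| 0.10 | 0.002 | 0.0017 | 33.9 | 33.96 |
| 0.20 | 0.035 | 0.0329 | 33.2 | 33.21 |
| 0.30 | 0.196 | 0.1959 | 29.9 | 29.93 |
| 0.40 | 0.549 | 0.5546 | 23.2 | 23.10 |
| 0.50 | 0.877 | 0.8751 | 15.5 | 15.48 |

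The quantiles also match. For example, at 0.50 the stopping probabilities by look are 0.3438, 0.2961, 0.0721, 0.0950 and 0.0681, so average N = 6(0.3438) + 12(0.2961) + 18(0.0721) + 24(0.0950) + 30(0.0681) + 34(1 − 0.8751) = 15.5.

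**Step 3: which rule Table 5 assumes.** The chance of at least 4 DLTs in the first 6 patients is 0.179 at a 40% rate and (15 + 6 + 1)/64 = 0.344 at 50%. Table 5 gives a 10th percentile of 6 patients at 40%, and 10th and 25th percentiles of 6 at 50%. If 4/6 did not end accrual, the smallest possible number at a stop would be 12. Table 5 therefore treats 4/6 as a permanent stop.

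**Step 4: the Section 1.6 rule.** The phrase about the first boundary can be read in two ways:

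- Narrow: only 4/6 at the first look triggers revision, and later boundaries halt.
- Broad: the first crossing at any look triggers revision, and only a later crossing halts.

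With DLT counts kept cumulative, P(stop) and average N are:

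| Rule | True rate 0.30 | 0.40 | 0.50 |
|---|---|---|---|
| Table 5 | 0.196; 29.9 | 0.549; 23.2 | 0.877; 15.5 |
| Narrow, rate unchanged | 0.174; 30.9 | 0.536; 24.8 | 0.869; 17.9 |
| Narrow, rate halved | 0.146; 31.5 | 0.457; 26.3 | 0.744; 20.6 |
| Broad, rate unchanged | 0.106; 32.4 | 0.411; 28.0 | 0.777; 21.7 |
| Broad, rate halved | 0.039; 33.4 | 0.186; 31.2 | 0.450; 26.9 |

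The counting convention matters too. If counts and boundaries restarted after revision (broad reading, rate unchanged), P(stop) would be 0.195 at 40% and 0.567 at 50%, against 0.411 and 0.777 with cumulative counts.

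**Step 5: low toxicity.** At 20%, Table 5 has average N 33.2 and P(stop) 0.035. Average N can therefore rise by at most 34 − 33.2 = 0.8, and P(stop) can fall by at most 3.5 percentage points. At 10% the room is smaller still.

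**The case against.** The best defence is that Section 1.6 is the specific instruction for the first listed boundary, 4/6, and that the later boundaries still halt. With the DLT rate unchanged, that reading moves P(stop) by at most 2.2 points (0.196 to 0.174, at 30%) and raises average N by at most 2.4 (15.5 to 17.9, at 50%). It is a fair reading of Section 1.6, but Section 8.1.3 lists 4/6 among the boundaries that halt the trial, and Table 5 is calculated that way. One could also take halting as a pause, since Section 8.1.2 uses the word in that sense for the futility interim. However, Section 8.1.3 also speaks of stopping early and describes no pause. If a pause is meant, P(stop) is still correct as the probability of a first crossing. That part of the defence stands.

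Safeguards also limit the consequence. Section 1.6 names who decides, Section 8.1.3 requires a toxicity summary after every six evaluable patients, and Section 9.4 requires IRB approval of protocol changes before they are implemented. They do not remove the contradiction, but they make it too strong to say that accrual could simply run on unreviewed.

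Three stronger readings might be inferred, and the documents support none of them:

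- **A cohort would always run to 34**, adding 34 − 15.5 = 18.5 patients at 50% toxicity or 34 − 23.2 = 10.8 at 40%. This sets an average against a maximum and assumes that no later boundary ever halts. Section 1.6 speaks only of the first.
- **DLTs and responses from two regimens would be pooled.** The documents are silent on this. It is a gap, not a stated rule.
- **Section 6.7.1 conflicts with the vaccine option in Section 1.6** because "MEDI0457 doses should not be modified". That sentence concerns managing toxicity in individual patients, while Section 1.6 concerns the number of doses at trial level.

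**Conclusion.** The point holds. Sections 1.6 and 8.1.3 state different consequences for the same crossing, and Table 5 is arithmetically right for the Section 8.1.3 rule only. The size ranges from minor to large. At 50% true toxicity, P(stop) lies between 0.869 and 0.450 against a stated 0.877, and average N between 17.9 and 26.9 against 15.5. At 40%, P(stop) lies between 0.536 and 0.186 against 0.549, and average N between 24.8 and 31.2 against 23.2. At 10% to 20% little changes on any reading.

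These ranges assume independent DLTs, cumulative counts, looks at exactly 6 to 30 patients, and a post-revision rate that is unchanged or halved. Like Table 5, they ignore futility stops and the selection of two cohorts for stage 2. In the halved-rate rows, part of the fall in P(stop) reflects lower toxicity after revision, so it is not in itself a loss of protection. The defect is that the stated operating characteristics may not belong to the rule that would be applied. No view is taken on which action or dose is right.

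**What to change.** Reconcile Sections 1.6 and 8.1.3 so that each boundary crossing has one stated consequence, and say to which cohorts it applies, given that cohorts are monitored independently. State how DLTs before and after any revision count toward the toxicity boundaries, and how responses before and after count toward 2/9 and 9/34. Then recompute Table 5 for the rule adopted. If a crossing is defined as a pause only, P(stop) may instead be relabelled as the probability of a first crossing. The average N and quantiles would then describe the point of first crossing, not total enrolment, and need the same relabelling or recalculation.

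The cost is protocol wording and a short calculation. P(stop) and average N may prove less favourable than now stated. If only patients on one regimen were to count toward 9/34, more patients would be needed to complete a cohort, so that choice should be costed when it is made.
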